6.3 Safety Assessments

6.3.1 Adverse Events

All AEs and SAEs will be collected from the time the subject signs the Informed Consent Form (ICF) until the final visit/contact with the subject. Additional safety information, including the definition of an AE and the methods for recording, evaluating, and assessing causality of AEs and the procedures for completing and transmitting SAE reports are provided in Section 8.

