13.2 Adverse Events

All AE summaries will be restricted to treatment-emergent AEs (TEAEs), which are defined as those AEs that occurred after dosing and those pre-existing AEs (prior to first application of study drug) that worsened during the study. If it cannot be determined whether the AE is treatment-emergent due to a partial onset date, then it will be counted as such. The one exception will be the summary of Any AE which will include AEs not considered treatment-emergent. The summary of Any AEs will be reported in the Overall Summary of Adverse Events.

Verbatim terms in the eCRFs will be mapped to SOCs and PTs using MedDRA (Version 24.0).

For subjects not rolling over to the OL-LTE safety study, all reported AEs will be included in the open-label maximal use summaries. For subjects rolling over to the OL-LTE safety study, all

AEs with an onset date on or before the Week 4 visit date will be included in the open-label maximal use summaries.

Imputation of Start and End Dates of Adverse Event

To calculate duration of AEs, the following rules will be used where applicable to impute partial or completely missing start dates or end dates:

- If only the day is missing for a start date, the 1st of the month will be imputed. If the new estimated date falls before the date of first dose, while the known month and year match the month and year of the first dose, the date of first dose will be used as the new estimated date. The AE will be considered as a treatment-emergent AE (TEAE).
- If only the day is missing for an end date, the last day of the month will be imputed. If the new estimated date falls after the date of last study visit, the date of last study visit will be used as the new estimated date. Last study visit is defined as the Week 4 visit for those who elect to participate in the OL-LTE safety study, or the Week 5 Follow-up Visit for those who fail to qualify for participation in the OL-LTE safety study, or who qualify to participate but ultimately elect not to enroll.
- If both the day and the month are missing for a start date or end date, no imputation will be used, and the duration will not be calculated. However, if the year of start is the same or greater than the year of the first dose date, the AE will be considered as a TEAE.
- If the start date or end date is completely missing, duration will not be calculated. However, an event with completely missing start date will be considered as a TEAE.

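### The adverse event start-date rules in SAP 13.2 have no end-date check, so an event known to have resolved before first dose can be counted as treatment-emergent

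*SAP*

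**What the plan says.** SAP 13.2 defines TEAEs as "those AEs that occurred after dosing and those pre-existing AEs (prior to first application of study drug) that worsened during the study". It then gives a default for incomplete onset dates: "If it cannot be determined whether the AE is treatment-emergent due to a partial onset date, then it will be counted as such".

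The imputation bullets follow. They are introduced as serving the calculation of AE duration, to be used where applicable.

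- **Day missing.** "If only the day is missing for a start date, the 1st of the month will be imputed". If that date is before first dose "while the known month and year match the month and year of the first dose", then "the date of first dose will be used as the new estimated date". The bullet closes with "The AE will be considered as a treatment-emergent AE (TEAE").
- **Day and month missing.** Nothing is imputed and no duration is calculated, but the event is a TEAE if its start year is the year of first dose or later.
- **Start wholly missing.** No duration is calculated, but "an event with completely missing start date will be considered as a TEAE".

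None of the three looks at the end date. Protocol 6.3.1 opens the collection window before dosing: "All AEs and SAEs will be collected from the time the subject signs the Informed Consent Form (ICF"). Screening can last up to 30 days.

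**The concern.** An event that starts and resolves during screening is not treatment-emergent, and its recorded end date proves it. The bullets never consult that date. For the day-missing case they also move the start to a day after the event was over.

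The Protocol lists the incidence, frequency and duration of TEAEs among its primary endpoints, and each age cohort has only about 12 subjects, so a single misclassified subject shows in a percentage. Events of special interest (AESIs) get a fuller summary in SAP 13.2, including earliest onset day and duration. Headache is one of them. A screening headache that resolved before dosing could appear as a treatment-emergent AESI with onset on Day 1 and an impossible duration.

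**Working it through.** The documents give no figure to reproduce here. The check applies the rule as written to illustrative dates.

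**Inputs**
- Start-date rule: SAP 13.2, day-missing bullet.
- Duration: SAP Appendix A, end date − start date + 1.
- Sample size: SAP 5, about 36 in total, about 12 and at least 10 per age cohort.
- Assumed for illustration: first dose 20 June, AE start recorded as June with the day unknown.

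**Step 1: imputed start.** The 1st of June is before 20 June and the month matches, so the start becomes 20 June and the event is a TEAE for every end date.

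**Step 2: date difference under the rule, and with an end-date check that keeps 1 June and drops TEAE status when the event ended before first dose.**

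| Known end date | Rule as written | With end-date check |
|---|---|---|
| 5 June | 5 − 20 + 1 = −14, TEAE | 5 − 1 + 1 = 5, not TEAE |
| 10 June | 10 − 20 + 1 = −9, TEAE | 10 − 1 + 1 = 10, not TEAE |
| 18 June | 18 − 20 + 1 = −1, TEAE | 18 − 1 + 1 = 18, not TEAE |
| 19 June | 19 − 20 + 1 = 0, TEAE | 19 − 1 + 1 = 19, not TEAE |
| 20 June | 20 − 20 + 1 = 1, TEAE | unchanged |
| 25 June | 25 − 20 + 1 = 6, TEAE | unchanged |

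Of the 19 possible end dates before first dose in that month, all 19 give a false TEAE. Eighteen give a negative difference, and the day before first dose gives 0. The extreme in a 31-day month (first dose on the 31st, end on the 1st) is 1 − 31 + 1 = −29.

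**Step 3: partial end dates.** In the day-missing rule, an end date known only to the same month is imputed to the last day of the month, or the last study visit if earlier. It gives no negative value, and it does not show that the event ended before dosing.

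**Step 4: the other two rules.** Neither calculates a duration. Each can still class an event as a TEAE when its end date, complete or known only to an earlier month, shows that it resolved before first dose.

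**Step 5: weight of one event.** SAP 13.2 counts a subject once at each level of summary, so any-TEAE incidence changes only if the subject has no other TEAE. In that case one event adds 1/12 = 8.3 percentage points, 1/10 = 10.0 at the minimum cohort size, and 1/36 = 2.8 overall.

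**Step 6: the section against itself.** An event over before first dose did not occur after dosing and cannot have worsened once treatment began. It fails both limbs of the definition. Its status can be determined, so the default for partial onset dates does not reach it. The day-missing and year-only bullets nevertheless call it a TEAE.

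**The case against.** The strongest reply is that SAP 13.2 already handles the case. The default to TEAE applies only where status cannot be determined, the bullets apply where applicable, and their stated purpose is duration. On that reading a careful programmer would leave out an event known to have ended before dosing. This stands in part: a reader might infer that the SAP plainly requires every such event to be counted, and the section as a whole does not support that. But the bullet states its classification without exception, so the two sentences pull apart and the right outcome is not secured. The limiting sentence also speaks only of partial onset dates, so it gives little help when the start is wholly missing.

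Second, Appendix A defines duration to a later second date, so −9 is the result of carrying the formula outside its scope and not an output the SAP prescribes. That is fair, but the SAP does not say what to do instead.

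Third, the reach is limited. The only duration summary that SAP 13.2 specifies is for AESIs. It uses each subject's maximum duration, so an impossible value shows only if that subject has no longer occurrence of the same AESI. Onset and end dates are listed for all AEs, and inconsistent data are queried. The study is single-arm and descriptive. All of this stands, and it keeps the point minor.

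Fourth, over-counting is conservative. Conservatism is a way to settle uncertainty, and for these events the end date leaves none.

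**Conclusion.** The point holds as a minor but real gap. The start-date rules lack an end-date check and conflict with the definition and the limiting sentence in the same section. Followed literally, the day-missing bullet yields a false TEAE with a zero or negative date difference. The year-only and wholly-missing rules can yield a false TEAE only.

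Three larger conclusions might be inferred, and the documents do not support them. Not every case gives a negative value: an end date one day before first dose gives 0, and two of the three rules calculate no duration. The 8.3 and 2.8 points are not automatic: they require a subject with no other TEAE. Nor is there a basis for saying that TEAE incidence will be materially inflated. The day-missing case needs an unknown start day, a start month equal to the first-dose month and a complete end date before first dose. The documents give no expected count, and the case is probably rare.

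The conclusion assumes that the bullets are programmed as written, and that worsening in the TEAE definition means worsening after dosing begins.

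**What to change.** In SAP 13.2, add to all three start-date rules: unless the complete or partial end date shows that the AE ended before the date of first dose, in which case the AE is not treatment-emergent.

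For the day-missing rule, also state which start date such an event keeps: the 1st of the month, or the consent date if that is later and not after the end date. No imputed start can then fall after the end date, and two programmers will derive the same duration. The choice matters. With an end date of 10 June, a start of 1 June gives 10 days, while an assumed consent date of 5 June gives 10 − 5 + 1 = 6 days.

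The SAP has precedents for such bounds: section 9.5 uses stop dates to separate prior from concomitant medications, and the end-date bullet in 13.2 caps the imputed end at the last study visit. Events ending on or after first dose are unaffected. The cost is a short edit to one section and a small condition in the AE derivation, with no new data collection.

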1.3.3 Overall Benefit Risk

Taking into account the measures taken to minimize risk to subjects in this study, the potential risks identified in association with tapinarof are justified by the anticipated benefits that may be afforded to subjects with AD.

2 Objectives and Endpoints

The objectives and associated endpoints of the study are as follows:

Objectives	Associated Endpoint
Primary	

To evaluate the safety and tolerability of tapinarof cream, 1% QD in pediatric subjects ages 2 to 17 years old with extensive ADTo evaluate the PK of tapinarof cream, 1% QD in pediatric subjects ages 2 to 17 years old with extensive AD	
Incidence, frequency and duration of TEAEs and serious adverse events (SAEs)Change from Baseline in laboratory valuesChange from Baseline in vital signsMean Investigator-assessed local tolerability scores (LTS) scores by visit (overall and sensitive areas)Tapinarof plasma PK parameters on Day 1, if data permit, including:
area under the plasma concentration versus time curve from time 0 to the last quantifiable concentration (AUC_{0-last})maximum plasma concentration (C_{max})time to maximum plasma concentration (t_{max})time of last quantifiable concentration (t_{last})Tapinarof plasma concentration on Day 28
Secondary	Secondary: 
To assess the efficacy of tapinarof cream, 1% QD in pediatric subjects ages 2 to 17 years old with extensive AD

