8.3.2 Follow-Up of Adverse Events

After the initial AE/SAE report, the Investigator is required to proactively follow each subject at subsequent visits/contacts. All SAEs and nonserious AEs will be followed until resolution, until the condition stabilizes, until the event is otherwise explained, or until the subject is lost to follow-up.

The Investigator will assess the outcome of each AE using the following criteria:

- **Recovered/Resolved:** The event has improved or subject recuperated.
- **Recovered/Resolved with sequelae:** The subject has recuperated but retained pathological conditions resulting from the prior disease or injury.
- **Recovering/Resolving:** The event is improving.
- **Not recovered/Not resolved:** The event has not improved or subject recuperated.
- **Unknown:** The outcome of the event is not known, not observed, not recorded, or refused.
- **Fatal:** Termination of life as an outcome of the AE.

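### The cap on day-missing AE end dates has no month check, so an event recorded as ending in a later month gets a contradictory date and too short a duration

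*SAP*

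**What the plan says.** SAP 13.2 introduces its date rules for one purpose: "To calculate duration of AEs, the following rules will be used where applicable". For end dates, the first step is "If only the day is missing for an end date, the last day of the month will be imputed". The second step is the cap: "If the new estimated date falls after the date of last study visit, the date of last study visit will be used". The cap has no condition on the recorded month or year.

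The start-date bullet directly above it does have one. A start date is moved to first dose only under this condition: "while the known month and year match the month and year of the first dose, the date of first dose will be used".

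The cap date depends on the subject's path: "Last study visit is defined as the Week 4 visit for those who elect to participate in the OL-LTE safety study". For subjects who do not qualify for the extension or choose not to enter it, it is the Week 5 Follow-up Visit. The definition does not mention subjects who terminate early.

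Three other places bear on the point:

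- Protocol 8.3.2 does not stop AE follow-up at the last visit: "All SAEs and nonserious AEs will be followed until resolution, until the condition stabilizes, until the event is otherwise explained".
- Protocol Section 2 lists duration of treatment-emergent and serious AEs among the primary endpoints.
- The AESI paragraph that closes SAP 13.2 summarises each subject's maximum duration and leaves out any AESI still ongoing at end of study.

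**The concern.** The protocol's follow-up rule makes end months after the Week 4 or Week 5 visit possible. For such an event with the day missing, the cap discards the one thing the site did record, the month, and substitutes a date in an earlier month. The error always shortens, and it affects only events that outlast the study.

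Two further consequences follow. The SAP has no rule that caps complete end dates, so two identical events get different durations only because one lacks a day. And an AESI with a later end month was by definition not resolved at the last visit, yet the capped date makes it look resolved on that day. The SAP does not say whether the ongoing-at-end-of-study exclusion is judged before or after imputation, so the event can enter the AESI duration summary with a short value instead of being left out.

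**Working it through.** The documents give no figure to reproduce. The check applies the rule literally. All calendar dates below are assumptions for illustration.

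**Inputs**

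- Imputed end date = the earlier of (last day of recorded month, last study visit), from SAP 13.2.
- Duration = end date − start date + 1, from SAP Appendix A.
- Last study visit = Week 4 for subjects entering the extension and Week 5 for the others, from SAP 13.2.

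**General result.** Let S be the start date, V the last visit and F the first day of the recorded end month, with that month later than the month of V. The rule gives V − S + 1. The shortest duration the record allows is F − S + 1. The shortfall is therefore at least F − V, which is always 1 day or more. Taking every date in 2022 as V, the imputed date fell outside the recorded month in 365 of 365 cases. The minimum shortfall was:

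| Recorded end month, relative to last-visit month | Minimum shortfall (days) |
|---|---|
| next month | 1–31 |
| two months later | 29–62 |
| three months later | 60–92 |
| six months later | 151–184 |

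**Example 1.** Onset 25 July, last visit 31 July.

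- SAP rule: 25 to 31 July = 7 days, whichever later month is recorded.
- End month August: 25 July to 1 August = 8 days, and to 31 August = 38. Possible range 8–38.
- End month September: 25 July to 1 September = 39 days, and to 30 September = 68. Possible range 39–68.

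**Example 2.** Onset 20 March. The last column caps only when the recorded month and year equal those of the last visit.

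| Last visit | Recorded end month | SAP rule | Possible range | Cap only if month and year match |
|---|---|---|---|---|
| Week 4, 28 March | March | 9 days | 1–12 | 9 days |
| Week 4, 28 March | April | 9 days | 13–42 | 42 days |
| Week 4, 28 March | May | 9 days | 43–73 | 73 days |
| Week 4, 28 March | September | 9 days | 166–195 | 195 days |
| Week 5, 4 April | May | 16 days | 43–73 | 73 days |

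When the recorded month is the month of the visit, the SAP rule gives a date inside that month and nothing is wrong.

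**Complete against partial dates.** In the April row, a complete end date of 10 April is left alone: 12 days (20 to 31 March) + 10 = 22 days. The same event with the day missing gets 9.

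**The case against.** **Reach.** The problem needs a record with the day alone missing and an end month after the last-visit month. The documents give no count, and about 36 subjects are planned. Whether end dates after rollover are entered in this study's case report form or in the extension's cannot be seen from the protocol and SAP. For an end month directly after the visit month, the minimum shortfall can be 1 day. All of this stands and limits the size of the point.

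**Primary endpoint.** A reader might infer that the primary safety results as a whole are biased. The documents do not support that. Duration is part of the endpoint, but SAP 13.2 summarises general treatment-emergent and serious AEs as incidence rates. The only duration summary it describes is the one for AESIs. Incidence, grade and relatedness do not use the imputed end date, and no hypothesis is tested.

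**The AESI exclusion.** If events are classed as ongoing before imputation, the affected AESIs never reach the summary and there is no bias in it. That is a fair reading, but the SAP sets no order between the two rules, so the outcome is left to the programmer.

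**Deliberate truncation.** The cap may be meant to cut durations off at the end of the study. The SAP does not say so, and it leaves complete later dates uncapped, so this reading does not rescue the rule.

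**End before start.** A reader might also infer that the rule will routinely produce end dates before start dates. It will not. Events counted for rollover subjects start on or before Week 4, and Protocol 6.3.1 and 8.3.1 collect AEs until the final visit or contact. It would take a rare onset after the last visit, in a non-rollover subject, with the end day missing.

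**Early termination.** The definition of last study visit omits these subjects, but SAP Section 4 already calls the Early Termination Visit their final visit. This is a small gap in wording, not a missing cap date.

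**Conclusion.** The point holds as a limited but definite error in a stated rule. For every AE with only the end day missing and an end month after the last-visit month, the imputed date contradicts the record and the duration is too short by at least the gap from the last visit to the first of the recorded month. An AESI of this kind can also appear as resolved in a summary that should exclude it.

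The size in any one record ranges from a day to several months; the number of records is unknown and probably small. The effect is confined to duration. The conclusion rests on the literal text of SAP 13.2, on the follow-up rule in Protocol 8.3.2, and on the assumption that end months after the last visit are entered in this study's data. The change should be made because the error is certain where it applies and costs little to remove.

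**What to change.** In SAP 13.2:

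1. Apply the last-visit cap only when the recorded end month and year equal those of the last study visit. Otherwise impute within the recorded month, and never before the AE start date.
2. State that an AE whose recorded end month is after the last-visit month counts as ongoing at end of study for the AESI duration summary. Without this, month-end imputation would put the top of the possible range into that summary (195 days in the September row above).
3. If truncation at the last visit is what is wanted, say so instead of items 1 and 2, and apply it to complete end dates as well.
4. Add the Early Termination Visit to the definition of last study visit, in line with SAP Section 4.

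The cost is a few sentences in SAP 13.2 and the matching lines in the AE dataset specification. No new data are needed.
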